9.4.1.1 Subgroup Analysis

An overview of all TEAEs and a summary of TEAEs by SOC and PT for the following subgroups will be provided:

- Age at screening (<18, ≥18 years)
- Percent predicted FEV₁ at baseline (<70, ≥70)
- Sex (male, female)
- Geographic Region (North America, Europe [including Australia])

9.4.2 Clinical Laboratory

For the treatment-emergent laboratory assessments, the observed values and change from baseline values of the continuous hematology, coagulation and chemistry results will be summarized in SI units at each visit by treatment group.

The number and percentage of subjects meeting at least 1 threshold analysis criterion event during the TE period will be summarized by treatment group. The threshold analysis criterion shift from baseline will also be summarized for selected laboratory parameters. The threshold analysis criteria are provided in [Appendix F](#).

For select LFT laboratory tests (alanine transaminase [ALT], aspartate transaminase [AST], alkaline phosphatase [ALP], and total bilirubin), a scatter plot of the maximum treatment-emergent value versus the baseline value corresponding to ×ULN (upper limit of normal) will be presented. Further, a scatter plot of the maximum treatment-emergent value of ALT and AST,

separately, versus the maximum treatment-emergent value of total bilirubin corresponding to \times ULN will also be presented by treatment group.

Results of positive urine/serum pregnancy test will be listed in individual subject data listings only. For positive serum pregnancy listing, subjects with serum HCG which are abnormally high will be selected.

In addition, a listing containing individual subject hematology, chemistry, and coagulation values will be provided. This listing will include data from both scheduled and unscheduled visits.

9.4.3 Electrocardiogram

For the treatment-emergent ECG measurements, a summary of observed values and change from baseline values will be provided at each visit by treatment group for the following ECG measurements (in msec): RR interval, PR interval, QT interval, and QTcF interval, QRS duration, and Heart Rate (beats per minute).

The number and percentage of subjects meeting at least 1 threshold analysis criterion during the TE period will be summarized by treatment group. The threshold analysis criteria are provided in [Appendix F](#).

9.4.4 Vital Signs

For the treatment-emergent vital signs measurements, the observed values and change from baseline values will be summarized at each visit by treatment group. The following vital signs parameters will be summarized: systolic and diastolic blood pressure (mm Hg), body temperature ($^{\circ}$ C), pulse rate (beats per minute), and respiratory rate (breaths per minute).

The number and percentage of subjects meeting at least 1 threshold analysis criterion during the TE period will be summarized by treatment group. The threshold analysis criteria are provided in [Appendix F](#).

9.4.5 Pulse Oximetry

For the treatment-emergent pulse oximetry measurements, a summary of observed values and change from baseline values will be provided at each visit by treatment group, for the percent of oxygen saturation by pulse oximetry.

The number and percentage of subjects with shift changes from baseline (normal/missing and low according to the reference range) to the lowest percent of oxygen saturation during the TE period will be summarized by treatment group.

9.4.6 Physical Examination

Abnormal PE findings will be presented as an individual subject data listing only.

9.4.7 Supportive Safety Analysis

9.4.7.1 Adverse Events of Special Interest

For this study, elevated transaminase events and rash events, as determined by MedDRA preferred terms in [Appendix G](#), are considered as adverse events of special interest.

For treatment-emergent elevated transaminase events and rash events, the following categories will be summarized by treatment group:

- Subjects with events

[figure not shown]
- Subjects with events by maximum severity
- Subjects with events leading to treatment discontinuation
- Subjects with events leading to treatment interruption
- Subjects with serious events
- Subjects with related serious events
- Subjects with events leading to death
- Duration of events
- Time-to-onset of first event

In addition, for treatment-emergent rash events, these categories will be summarized for the following subgroups:

- Sex (male, female)
- Female subjects with concomitant hormonal therapy (Yes, No)

9.4.7.2 Hormonal Therapy

The number of subjects who used hormonal therapy concomitantly will be summarized by treatment group based on the Safety Set.

10 SUMMARY OF INTERIM AND DMC ANALYSIS

For each DMC meeting and the planned IA, the Vertex Biometrics Department will prepare the analysis package using the dummy treatment code and dummy spirometry and SwCl data according to the DMC charter and the DMC SAP, respectively; SAS (Version 9.4, or higher) will be used to generate all statistical outputs (tables, figures, listings, and datasets).

████████████████████, appointed as the independent biostatistician, will perform the IA according to the DMC SAP using the SAS code provided by Vertex Biometrics Department, the unblinded treatment code, the real (restricted) spirometry, and the real (restricted) sweat chloride data. Unblinded treatment code, spirometry, and sweat chloride data will be transferred directly from relevant vendors to the independent biostatistician. ██████ will present the results to the DMC.

If the study crosses the efficacy boundary according to the pre-specified criterion (Section 7.5), a limited Vertex unblinded team may be unblinded to the study. The limited Vertex unblinded team will use the unblinded treatment code and real (restricted) data to generate statistical outputs and prepare for submission(s). Members of the limited Vertex unblinded team will not be involved in or influence the conduct of the remaining part of the study to protect the integrity of the study.

10.1 Interim Analysis

10.1.1 General Consideration

Refer to Section 7.5 for the timing of the IA. General considerations, reporting conventions, and analysis methods specified for the final analysis apply to the IA, unless otherwise specified.

For the IA purpose, the **treatment-emergent (TE) period** will include the time from the first dose of study drug in the Treatment Period until 28 days after the last dose of study drug, or the study participation end date, or the IA data cutoff date, whichever occurs first.

10.1.2 Background Characteristics

10.1.2.1 Subject Disposition

The number of subjects in the following categories will be summarized:

- All Subjects Set
- Interim Full Analysis Set
- IA Safety Set
- Safety Set
- Randomized
- Randomized but not dosed

The number and percentage (based on the iFAS) of subjects in each of the following disposition categories will be summarized by treatment group and overall:

- Completed Week 4 Visit
- Prematurely discontinued treatment before Week 4 Visit and the reason for discontinuation
- Completed Week 12 Visit
- Prematurely discontinued treatment before Week 12 Visit and the reason for discontinuation
- Completed treatment
- Prematurely discontinued treatment and the reason for discontinuation
- Completed study
- Prematurely discontinued the study and the reason for discontinuation
- Rollover to open-label study

A listing will be provided for subjects who discontinued treatment or who discontinued study with reasons for discontinuation.

10.1.2.2 Demographics and Baseline Characteristics

The same demographics and baseline characteristics specified in Section 9.2.2 will be summarized based on the iFAS.

10.1.2.3 Study Drug Exposure

For the purpose of the IA, the study drug exposure will be calculated using the same approach specified in Section 9.2.5. For subjects who are still on study drug at the IA data cutoff date, the IA data cutoff date will be used as the last dose date for the exposure calculation.

Exposure summaries will be provided for subjects in the IA Safety Set as well as for subjects in the Safety Set who had been on-study for ≥ 12 weeks, and will be presented by treatment group and overall.

10.1.3 Efficacy Analysis

All efficacy analyses described in this section will be based on the iFAS, unless otherwise specified.

10.1.3.1 Analysis of Primary Efficacy Variable

The analysis of the primary efficacy variable of absolute change in ppFEV₁ from baseline at Week 4 will be performed using an MMRM with change from baseline at Day 15 and Week 4 as the dependent variable. The model will include treatment group, visit, and treatment by visit interaction as fixed effects, with continuous baseline ppFEV₁, age at screening (<18 versus ≥ 18 years of age) and sex (male versus female) as covariates. The model will be estimated using restricted maximum likelihood. Denominator degrees of freedom for the *F*-test for fixed effects will be estimated using the Kenward-Roger approximation². An unstructured covariance structure will be used to model the within-subject errors. If the model estimation does not converge, a compound symmetry covariance structure will be used instead. Conditional on the observed data and covariates, missing data will be assumed to be missing at random; consequently, no imputation of missing data will be performed.

The sensitivity analysis based on the multiple imputation (Section 9.3.1.4) will be performed during the IA, if $\geq 10\%$ of the subjects have missing change in ppFEV₁ at Week 4 in any treatment group. However, since the analysis model uses the change from baseline at Day 15 and Week 4 as the dependent variable, the primary timepoint for imputation will be Week 4 and only data up to the Week 4 Visit will be used in the imputation.

Subgroup analyses of the primary efficacy variable will also be performed during the IA in a manner similar to that of the primary analysis (Section 9.3.1.5) for each of the following subgroups using data up to the Week 4 Visit:

- Age at screening (<18, ≥ 18 years)
- Percent predicted FEV₁ at baseline (<70, ≥ 70)
- Sex (male, female)
- Geographic region (North America, Europe [including Australia])

10.1.3.2 Analysis of Key Secondary Efficacy Variable

The following key secondary efficacy variables defined in Section 9.3.2.1 will be analyzed during the IA using an ANCOVA model:

- Absolute change in SwCl from baseline at Week 4
- Absolute change in CFQ-R respiratory domain score from baseline at Week 4

The model will use the change from baseline value at Week 4 as the dependent variable and include treatment group as fixed effects with continuous baseline ppFEV₁, age at screening (<18 versus ≥ 18 years of age), and sex (male versus female) as covariates. The estimated treatment difference at Week 4, the adjusted means with 2-sided 95% confidence intervals and nominal 2-sided *P* values will be provided.

Analyses of other efficacy and/or pharmacodynamic variables may be performed if the data are deemed sufficient.

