12.3.3.1.2 Analysis of Secondary Variables

Analysis of Key Secondary Variables

The key secondary efficacy variables include:

- **Absolute change in ppFEV₁ through Week 24:** Analysis of this variable will be based on an MMRM model that is exactly the same as the primary efficacy variable. Data obtained from the Day 15, Week 4, Week 8, Week 12, Week 16, and Week 24 Visits will be included in the model, however, the Day 15 Visit will not be included in the estimation of the average treatment effect through Week 24.
- **Number of PEx through Week 24:** Analysis of this variable will be performed using a negative binomial regression model with a fixed effect for treatment, as well as continuous baseline ppFEV₁, age at screening (<18 versus ≥18 years of age), and sex (male versus female) as covariates. The logarithm of the subject-specific PEx analysis period duration (defined in the SAP) will be treated as the offset in the model.
- **Absolute change in SwCl from baseline through Week 24:** Analysis of this PD variable will be based on an MMRM model similar to the analysis of the primary efficacy variable. Data obtained from Week 4, Week 8, Week 12, and Week 24 Visits will be included in the model and all of these visits will be included in the estimation of the average treatment effect through Week 24.
- **Absolute change in the CFQ-R respiratory domain score from baseline through Week 24:** Analysis of this domain will be based on an MMRM model similar to the analysis of the primary efficacy variable. Data obtained from Week 4, Week 8, Week 12, Week 16, and Week 24 Visits will be included in the model and all of these visits will be included in the estimation of the average treatment effect through Week 24.
- **Absolute change in BMI from baseline at Week 24:** Analysis of this variable will be based on an MMRM model similar to the analysis of the primary efficacy variables. Data obtained from Day 15, Week 4, Week 8, Week 12, Week 16, and Week 24 Visits will be included in the model.
- **Absolute change in SwCl from baseline at Week 4:** Analysis of this variable will be based on an MMRM similar to the analysis of the primary efficacy variable. Data obtained from Week 4, Week 8, Week 12, and Week 24 Visits will be included in the model to estimate the treatment effect at Week 4.

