9.2.2 Demographics and Baseline Characteristics

Demographics and baseline characteristics will be summarized by treatment group and overall based on the FAS.

Demographic data will include the following:

- Age at baseline (in years)
- Sex (male, female)
- Ethnicity (Hispanic or Latino, not Hispanic or Latino, and not collected per local regulations)
- Race (White, Black or African American, Asian, American Indian or Alaska Native, Native Hawaiian or Other Pacific Islander, Other, and not collected per local regulations)
- Geographic region (North America, Europe [including Australia])

Baseline characteristics will include the following:

- Weight (kg)
- Height (cm)
- BMI (kg/m²)
- BMI z-score (for subjects ≤ 20 years old at Baseline)

Stratification categories (in addition to sex) will include the following:

- Age at the Screening Visit (<18, and ≥ 18 years)
- ppFEV₁ determined during the Screening Period (<70, and ≥ 70)

Disease characteristics will include the following:

- ppFEV₁ at baseline (<40, ≥ 40 to <70, ≥ 70 to ≤ 90 , and >90)
- ppFEV₁ at baseline (continuous)
- Sweat chloride at baseline (continuous)
- CFQ-R respiratory domain score at baseline (continuous)
- Prior use of dornase alfa (Yes, No)
- Prior use of azithromycin (Yes, No)
- Prior use of inhaled antibiotic (Yes, No)
- Prior use of any bronchodilator (Yes, No)
- Prior use of any inhaled bronchodilator (Yes, No)
- Prior use of any inhaled hypertonic saline (Yes, No)
- Prior use of any inhaled corticosteroids (Yes, No)

- Infection with *Pseudomonas aeruginosa* within 2 years prior to screening (Positive, Negative)

In addition, data listings will also be provided for:

- Informed consent;
- Inclusion/Exclusion criteria violation for subjects with any such violations.

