9.3.1.2 Primary Analysis

The primary analysis will be performed using a mixed-effects model for repeated measures (MMRM) with change from baseline at Day 15, Week 4, Week 8, Week 12, Week 16, and Week 24 as the dependent variable. The model will include treatment group, visit, and treatment by visit interaction as fixed effects, with continuous baseline ppFEV₁, age at screening (<18 versus ≥18 years of age) and sex (male versus female) as covariates. The model will be estimated using restricted maximum likelihood. Denominator degrees of freedom for the *F*-test for fixed effects will be estimated using the Kenward-Roger approximation². An unstructured covariance structure will be used to model the within-subject errors. If the model estimation does not converge, a compound symmetry covariance structure will be used instead. Conditional on the observed data and covariates, missing data will be assumed to be missing at random; consequently, no imputation of missing data will be performed.

The primary result obtained from the model will be the estimated treatment difference at Week 4. The adjusted means with 2-sided 95% confidence intervals and 2-sided *P* values will be provided. Furthermore, the treatment difference at each post-baseline visit obtained from the model will also be provided.

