9.3.1.5 Subgroup Analysis

Subgroup analyses of the primary efficacy endpoint will be performed using a model similar to that of the primary analysis for each of the following subgroups:

- Age at screening (<18, ≥18 years)
- Percent predicted FEV₁ at baseline (<70, ≥70)
- Sex (male, female)
- Geographic region (North America, Europe [including Australia])
- Prior use of inhaled antibiotic (Yes, No)
- Prior use of dornase alfa (Yes, No)
- Prior use of inhaled bronchodilator (Yes, No)
- Prior use of inhaled hypertonic saline (Yes, No)
- Prior use of inhaled corticosteroids (Yes, No)
- Prior use of azithromycin (Yes, No)
- Infection with *Pseudomonas aeruginosa* within 2 years prior to screening (Positive, Negative)

The MMRM used for the primary analysis will be used for the subgroup analysis, where the same model will be applied to each category of the subgroup. Note that for the subgroup analysis based on age and sex, the covariate of age at screening (<18 versus ≥18 years of age) and sex (male versus female) from the MMRM will be removed, respectively. The adjusted means with 2-sided 95% confidence intervals will be provided. Furthermore, the estimated treatment difference at Week 4 in different categories within a subgroup will also be presented in a forest plot. Note: The results from the subgroup analysis should be interpreted with caution in the cases where sample sizes are small.

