9.3.2.2 Analysis Method

Absolute change in ppFEV₁ through Week 24: Analysis of this variable will be based on an MMRM that is exactly the same as the primary efficacy variable. However, the Day 15 Visit will not be included in the estimation of the average treatment effect through Week 24 as the treatment effect is not expected to reach the steady state at Day 15.

Number of PEx through Week 24: Analysis of this variable will be performed using a negative binomial regression model with a fixed effect for treatment, as well as continuous baseline ppFEV₁, age at screening (<18 versus ≥18 years of age), and sex (male versus female) as covariates. The logarithm of the subject-specific PEx analysis period duration (in years) will be treated as the offset in the model.

Absolute change in SwCl from baseline through Week 24: Analysis of this PD variable will be based on an MMRM similar to the analysis of the primary efficacy variable. Data obtained from Week 4, Week 8, Week 12, and Week 24 Visits will be included in the model and all of these visits will be included in the estimation of the average treatment effect through Week 24.

Absolute change in the CFQ-R respiratory domain score from baseline through Week 24: Analysis of this domain will be based on an MMRM similar to the analysis of the primary efficacy variable. Data obtained from Week 4, Week 8, Week 12, Week 16, and Week 24 Visits will be included in the model and all of these visits will be included in the estimation of the average treatment effect through Week 24.

Absolute change in BMI from baseline at Week 24: Analysis of this variable will be based on an MMRM similar to the analysis of the primary efficacy variable. Data obtained from Day 15, Week 4, Week 8, Week 12, Week 16, and Week 24 Visits will be included in the model.

Absolute change in SwCl from baseline at Week 4: Analysis of this PD variable will be based on an MMRM similar to the analysis of the primary efficacy variable. Data obtained from Week 4, Week 8, Week 12, and Week 24 Visits will be included in the model to estimate the treatment effect at Week 4.

Absolute change in CFQ-R respiratory domain score from baseline at Week 4: Analysis of this domain will be based on an MMRM similar to the analysis of the primary efficacy variable. Data obtained from Week 4, Week 8, Week 12, Week 16 and Week 24 Visits will be included in the model to estimate the treatment effect at Week 4.

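### The interim ANCOVA for sweat chloride and CFQ-R leaves out each outcome's own baseline, and the final MMRMs probably do too; the cost is precision only, and adding the term is nearly free

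*SAP*

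**What the plan says.** **Interim analysis.** SAP 10.1.3.2 analyses change from baseline at Week 4 in SwCl and in CFQ-R respiratory score by ANCOVA. The model will "include treatment group as fixed effects with continuous baseline ppFEV₁, age at screening" (under 18 versus 18 and over) and sex. Protocol 12.3.3.2.2 has the same list. Both baselines are available: the disease characteristics in SAP 9.2.2 include entries that begin "Sweat chloride at baseline (continuous" and "CFQ-R respiratory domain score at baseline (continuous".

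**Final analysis.** The primary MMRM (SAP 9.3.1.2) has treatment, visit and "treatment by visit interaction as fixed effects, with continuous baseline ppFEV₁, age at screening" group and sex. For SwCl, SAP 9.3.2.2 says: "Analysis of this PD variable will be based on an MMRM similar to the analysis of the primary efficacy variable". Protocol 12.3.3.1.2 agrees: "Analysis of this PD variable will be based on an MMRM model similar to the analysis of the primary efficacy variable". CFQ-R (through Week 24 and at Week 4) and BMI at Week 24 are described in the same way. Visits are listed for each of these five endpoints; covariates are not. Only ppFEV₁ through Week 24, which has the same dependent variable, is said to use exactly the primary model.

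**The concern.** In the primary model, baseline ppFEV₁ is the outcome's own baseline. Carried over to SwCl or CFQ-R it is not, and nothing else in the list takes that role. A change score that is not adjusted for its own baseline usually has a larger variance than one that is, so intervals are wider than the data require.

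At the interim, the affected results are descriptive. At the final analysis, the five endpoints are steps 3 to 7 of the fixed sequence (SAP 9.3.2.3), so if the final models share the omission, the lost precision falls on confirmatory tests.

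**Working it through.** **1. What the documents settle.** The interim list is closed and identical in both documents, so the omission there is certain. For the final models the texts have to be read together:

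- SAP 9.3.1.5 describes the subgroup analyses as "using a model similar to that of the primary analysis", then explains: "where the same model will be applied to each category of the subgroup". It names each covariate removed. But the outcome there is still ppFEV₁, so a change of baseline never arises.
- SAP 9.3.3.2 (BMI z-score) states that the age covariate is dropped and mentions no change of baseline.
- SAP 10.1.3.2 is the only place where covariates for SwCl and CFQ-R are written out, and it uses ppFEV₁.
- No supplied text names own baseline as a covariate for any of the five endpoints.

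Omission is therefore the more likely reading, but it is not stated.

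**2. Inputs.** The visible text gives no SD, correlation or power for SwCl, CFQ-R or BMI, so there is no planning figure to reproduce. All correlations below are assumptions. Visit numbers come from SAP 9.3.2.2: 4 for SwCl through Week 24 and 5 for CFQ-R.

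**3. Formula.** Set baseline SD to 1 and follow-up SD to k. Average m follow-up visits that correlate rb with baseline and rf with each other. The variance of the follow-up average is vF = k²(1 + (m − 1)rf)/m. Then

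- without own baseline, the variance is proportional to vF + 1 − 2·rb·k;
- with own baseline, it is proportional to vF − rb²k².

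The ratio (with over without) is (vF − rb²k²)/(vF + 1 − 2·rb·k).

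**4. Single visit, equal SDs (m = 1, k = 1).** The ratio reduces to (1 − ρ²)/(2 − 2ρ) = (1 + ρ)/2.

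| ρ | variance ratio | interval width ratio |
|---|---|---|
| 0.3 | 0.65 | 0.81 |
| 0.5 | 0.75 | 0.87 |
| 0.7 | 0.85 | 0.92 |
| 0.9 | 0.95 | 0.97 |
| 0.98 | 0.99 | 0.99 |

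The last two rows are the assumed range for BMI and weight.

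**5. Average through Week 24, equal SDs.**

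| rb | rf | SwCl (m = 4) | CFQ-R (m = 5) |
|---|---|---|---|
| 0.5 | 0.5 | 0.375/0.625 = 0.60 | 0.35/0.60 = 0.58 |
| 0.5 | 0.7 | 0.525/0.775 = 0.68 | 0.51/0.76 = 0.67 |
| 0.5 | 0.9 | 0.675/0.925 = 0.73 | 0.67/0.92 = 0.73 |
| 0.7 | 0.7 | 0.285/0.375 = 0.76 | 0.27/0.36 = 0.75 |
| 0.7 | 0.9 | 0.435/0.525 = 0.83 | 0.43/0.52 = 0.83 |

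**6. Where there is no gain.** If the slope of follow-up on baseline (rb·k) is 1, the ratio is 1. Example: k = 1.25, ρ = 0.8, m = 1 gives 1.5625 × 0.36 = 0.5625 over 1 + 1.5625 − 2 = 0.5625.

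**7. Does baseline ppFEV₁ recover the loss?** The interim ANCOVA was simulated with 70 per arm, 4,000 runs, and ppFEV₁, age group and sex in both models. Variance ratios at ρ 0.3, 0.5, 0.7 and 0.9 were 0.66, 0.75, 0.84 and 0.95 with ppFEV₁ unrelated to the outcome, and 0.58, 0.69, 0.83 and 0.94 with a correlation of 0.4. It does not recover the loss. Mean error was near zero in both models.

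**8. Cost of the term.** The model goes from 5 to 6 parameters: (140 − 5)/(140 − 6) = 1.0075, about 0.8% of variance, and (360 − 5)/(360 − 6) = 1.0028, about 0.3%.

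**The case against.** The best defence is that the covariate set has its own logic. Randomisation is stratified by screening ppFEV₁, age group and sex (SAP 7.3), and the models carry those factors, with ppFEV₁ as continuous baseline. The same set appears in the primary MMRM, the negative binomial model, the Cox model and the interim ANCOVA. On this view ppFEV₁ is there as a stratification covariate, and no own-baseline principle was broken. That stands: the analyses are prespecified and valid, and adding own baseline is a matter of efficiency.

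It is also fair that the certain part decides nothing, because the interim P values for SwCl and CFQ-R are nominal, and that the consequential part is inferred. *Similar* contrasts with the exact identity claimed for ppFEV₁ through Week 24, and could mean that each outcome's own baseline takes the place of ppFEV₁. The subgroup section cannot settle this. SAP Version 1.1 EUR and Addendum 1, both cited in Addendum 2, were not supplied and may do so.

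What survives is narrow. The interim omission is explicit and no reason is given. If *similar* does mean own baseline, the interim and final Week 4 models differ without explanation, and whether own baseline replaces ppFEV₁ or joins it is left open.

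**Conclusion.** The point holds as a free improvement of minor weight. The omission is certain for the interim ANCOVA and probable, but not stated, for the five final MMRMs. With equal SDs, own-baseline adjustment would multiply the variance at a single visit by 0.65 to 0.85 (ρ 0.3 to 0.7), and that of the SwCl average through Week 24 by about 0.60 to 0.83 (baseline correlation 0.5 to 0.7, between-visit correlation 0.5 to 0.9). For BMI and weight there is almost nothing to gain.

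Four stronger readings are tempting and are not supported:

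- *Bias or inflated type I error.* Under randomisation both models are unbiased. Chance imbalance in the outcome's own baseline has expectation zero, and its variance is already in the ratios, so it is not a second harm.
- *Endpoints at risk in the hierarchy.* The visible text gives no power for SwCl, CFQ-R or BMI. The sample size was set for exacerbations, which stand at step 2 with about 80% power (SAP 7.2). Any power gain quoted for steps 3 to 7 would need an invented starting value.
- *A variance reduction of 40% or more as the expected gain.* In the cases shown, that needs follow-up visits to correlate with each other no more than with baseline. At rb 0.5, raising rf from 0.5 to 0.9 moves the SwCl ratio from 0.60 to 0.73.
- *An effect on the interim efficacy decision.* The boundary uses ppFEV₁ only, whose model already contains its own baseline.

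**What to change.** - **SAP 10.1.3.2:** add baseline SwCl or baseline CFQ-R respiratory score, respectively, to baseline ppFEV₁, age group and sex.
- **SAP 9.3.2.2:** for each of the five final MMRMs, write out the covariates in place of the reference to the primary model, and add that outcome's own continuous baseline. For SwCl and CFQ-R this is where the gain lies; for BMI it is mainly consistency.
- **Protocol 12.3.3.1.2 and 12.3.3.2.2:** align them, or record the change in SAP 3.1, which now reads as not applicable. Do this before the relevant data lock and unblinding.

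The cost is one term per model, about 1 degree of freedom (0.8% of variance at 140 subjects, 0.3% at 360). No new data are needed, and no subject is lost, because a subject without that baseline has no change score.
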